**Table 3 Alpha Spending for Interim Analyses**

Interim #	CI %	Nominal $\alpha$	Cumulative $\alpha$
1	99.7%	0.003	0.003
2	96.5%	0.035	0.036
3	92.3%	0.077	0.087
4	88.8%	0.112	0.139
Final Analysis	84.5%	0.155	0.200

The effect of this futility analysis on the overall power of the study is small, but non-zero. There is a 0.6% chance of stopping the study for futility if the actual difference in 28 day mortality is 8% in favor of treatment (16% vs. 24%).

Interim analysis outputs will be programmed initially using dummy treatment codes by a blinded biostatistics team. The programs will be sent to the unblinded statistician supporting the DMC and rerun using the actual unblinded treatment codes. All interim analysis outputs will be based upon the randomized treatment assignments.

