10.3.3 Stopping Due to Lack of Clinically Meaningful Benefit/Futility

An analysis to rule out clinically meaningful benefit will also be performed. The goal of these analyses is to stop the study if sufficient evidence exists that there is not a clinically meaningful treatment benefit. The futility analyses will be conducted with the use of a lower O'Brien-Fleming type boundary. This boundary will be constructed using a one-sided alpha level of 0.20 and the hypothesis: the 28-day mortality rate on ART-123 is reduced by 6%. Should interim analyses be performed after the 600 subjects time-point (75% information) the DMC will interpret the results of the futility calculations in context of the remaining enrollment.

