### **2.3 Sample Size**

The primary analysis for this study will be based on a stratified Cochran-Mantel-Haenszel test. For sample size and power calculations a Chi-squared test has been used. A sample size of 800 subjects provides approximately 80% power if the following assumptions are made:

1. 5% two-sided alpha level
2. 8% treatment effect (24% placebo mortality rate vs. 16% ART-123 mortality rate).
3. 1 to 1 randomization

The assumed treatment effect and mortality rates are based upon post-hoc results from study 2-001 and assume the day 28 mortality status will be known for all subjects.

A sample size of 800 subjects and these assumptions also provides 32% power for a 0.1% two-sided  $\alpha$  level. If the true treatment effect is 12% (24% vs. 12%), a sample size of 800 provides greater than 80% power when a 0.1% alpha level is used.

In this 800 subject study, an observed treatment benefit of approximately 6% is expected to result in a p-value less than 5% and a difference of approximately 9% is expected to result in a p-value less than 0.1%.

The sample size and power calculations were performed with Pass 2007.

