### 3.8 Interim Analysis

This study will include un-blinded interim analysis (IA) performed by a Data Monitoring Committee. There will be 4 IAs planned to occur when 150, 300, 450 and 600 subjects are evaluable for the 28 day all-cause mortality endpoint.

The DMC may recommend termination or modification of the study based upon a review of the totality of the data. Early termination of the study for efficacy will not be actively pursued however guidelines regarding this are provided in [Section 5](#).

Analyses to rule out clinically meaningful benefit will also be performed. The goal of these analyses is to stop the study if sufficient evidence exists that there is not a clinically meaningful treatment benefit. The futility analyses will be conducted with the use of a lower O'Brien-Fleming-type boundary. This boundary will be constructed using a one-sided alpha level of 0.20 and will test the hypothesis given below:

$$H_o : M_{ART} < M_{plb} - 6\%$$
$$H_a : M_{ART} \geq M_{plb} - 6\%$$

Confidence intervals will be used to evaluate these hypotheses as outlined in [Section 5](#).

Termination or modification of the study due to safety concerns will not be limited to a fixed set of analyses.

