## 5 Interim Analysis

Only subjects randomized prior to the DMC database lock date (i.e., 8 weeks prior to the DMC meeting) will be considered evaluable for the primary efficacy and futility analyses at each of the interim analyses.

Early termination of the study for efficacy will not be actively pursued. However, should the primary efficacy results surpass an O'Brien-Fleming type boundary using a two-sided alpha level of 0.001 and the DMC believes the study results are extremely robust and so positive it is unethical to continue the study they may recommend termination of the study for efficacy. The alpha level for this O'Brien-Fleming boundary has been selected to result in a negligible impact on both decision rules outlined in [Section 2.2](#). The impact on the final alpha level at the 0.1% level is very small but is non-zero. The alpha spent at the interim analysis is approximately 0.00005. Due to the small size of this alpha spend no adjustment to final alpha level will be made.

Early termination for futility will be assessed using a Mantel-Haenszel difference of proportions with pooled site as a stratification factor. If the lower bound of the confidence interval around the difference of proportions ( $M_{ART} - M_{PIb}$ ) exceeds -0.06 then this will be considered sufficient evidence to rule out clinically meaningful benefit. The alpha spending rule and corresponding confidence interval that will be produced for each DMC plus the final analysis will use a Lan-DeMets approach. [Table 3](#) is an example of how the alpha spending would look if the interims occurred at 150, 300, 450 and 600 subjects as planned.

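### SAP Section 5 gives a 0.6% chance of a futility stop at the design effect (16% vs 24%); its own Table 3 boundary gives about 4.8%, and 0.6 points is the loss of power

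*SAP*

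**What the plan says.** The futility rule is set out in three places.

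- Protocol 10.3.3 and SAP 3.8 both use a lower O'Brien-Fleming-type boundary at one-sided 0.20 against the hypothesis of a 6-point mortality reduction. In SAP 3.8: "This boundary will be constructed using a one-sided alpha level of 0.20". SAP 3.8 plans four interims, at 150, 300, 450 and 600 evaluable subjects.
- SAP Section 5 gives the criterion, which begins "If the lower bound of the confidence interval around the difference of proportions" (ART-123 minus placebo) and is met when that bound is above -0.06. Spending follows Lan-DeMets. Table 3 "is an example of how the alpha spending would look if the interims occurred at 150, 300, 450 and 600 subjects as planned".
- The text after Table 3 describes the consequences. It says "The effect of this futility analysis on the overall power of the study is small, but non-zero", and then "There is a 0.6% chance of stopping the study for futility if the actual difference in 28 day mortality is 8" per cent (16% vs 24%).

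The 8-point effect is the sample-size assumption in SAP 2.3: "8% treatment effect (24% placebo mortality rate vs. 16% ART-123 mortality rate").

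**The concern.** The boundary spends 0.139 of one-sided error by the fourth interim if the true benefit is 6 points. The design effect of 8 points is only 2 points further away, and the standard error of the difference is 2.8 points even at 800 subjects. A fall in the stopping chance from 13.9% to 0.6% over so small a shift is not credible.

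The sentence is the SAP's only figure for how often the rule would end the trial when the drug works as assumed. A data monitoring committee or sponsor relying on it would put that chance at about 1 in 170 (1/0.006), when it is about 1 in 20. That affects how a crossing is interpreted.

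**Working it through.** **Inputs.** 800 subjects, 1:1, 24% vs 16%, all day 28 statuses known (SAP 2.3). Looks at 150, 300, 450 and 600 (SAP 3.8), so the information fractions t are 0.1875, 0.375, 0.5625, 0.75 and 1. One-sided 0.20 and margin -0.06 (SAP 3.8 and 5). Nominal alphas from Table 3.

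**1. Design power reproduces.** The two-proportion normal approximation with 400 per arm gives 80.9% at two-sided 5% and 32.1% at 0.1%. SAP 2.3 states about 80% and 32%.

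**2. Table 3 reproduces.** The cumulative spend is 2 - 2Φ(z₀.₉₀/√t). Recursive integration then gives the nominal levels.

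| Look | Cumulative, Table 3 | Cumulative, computed | Nominal, Table 3 | Nominal, computed |
|---|---|---|---|---|
| 150 | 0.003 | 0.0031 | 0.003 | 0.0031 |
| 300 | 0.036 | 0.0364 | 0.035 | 0.0354 |
| 450 | 0.087 | 0.0875 | 0.077 | 0.0767 |
| 600 | 0.139 | 0.1389 | 0.112 | 0.1118 |
| 800 | 0.200 | 0.2000 | 0.155 | 0.1553 |

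The printed nominal alphas are therefore one-sided levels, and the boundary is not in dispute.

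**3. A hand check on the fourth interim alone.** The standard error at 600 is √[(0.16×0.84 + 0.24×0.76)/300] = √(0.3168/300) = 0.0325. One-sided 0.112 corresponds to z = 1.216. The lower bound is above -0.06 when the observed difference is above -0.06 + 1.216×0.0325 = -0.0205. If the true difference is -0.08, this needs a deviation of 0.0595/0.0325 = 1.83 standard errors, which has probability 3.4%. The chance of crossing at any of four looks cannot be below the chance of crossing at one of them, so 0.6% is ruled out already.

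**4. All four interims.** The standard error at 800 is √(0.3168/400) = 0.02814, and the drift is (-0.08 + 0.06)/0.02814 = -0.711. Cumulative crossing with the printed nominal alphas:

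| Through look | Integration | Binomial simulation (1,000,000 trials) |
|---|---|---|
| 150 | 0.11% | 0.15% |
| 300 | 1.28% | 1.38% |
| 450 | 3.05% | 3.14% |
| 600 | 4.74% | 4.89% |

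A separate simulation of 2,000,000 trials gives 4.84%. The ratio to the stated figure is 4.84/0.6 = 8.1.

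**5. Loss of power.** In the 2,000,000-trial simulation, power at two-sided 5% is 81.14% without the rule and 80.56% with it, a loss of 0.58 points. Of the stopped trials, 12.0% would have reached p<0.05 at 800 subjects, and 4.84% × 0.120 = 0.58%. The other 88% would have missed it.

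**6. Could another schedule or effect give 0.6%?** With the spend recomputed for each schedule:

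| Looks | Crossing at 16% vs 24% |
|---|---|
| 140/280/420/560 | 4.3% |
| 165/330/495/660 | 5.3% |
| 300/600 | 4.6% |
| 600 only | 4.5% |
| 150/300/450 only | 3.0% |

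With the planned looks, interim stopping falls to 0.6% only at a true benefit of about 10.8 points (24% vs 13.2%).

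**The case against.** The strongest argument concerns how the intervals are read. Section 5 speaks of the lower bound of a confidence interval, Table 3 prints interval percentages, and Protocol Section 10 generally reports two-sided intervals. A programmer who built the printed intervals as two-sided would get interim stopping of 2.1% to 2.2%, about 3.6 times the stated figure and not eight times. On that reading, cumulative crossing through the second interim alone is about 0.6%, so the power loss is not the only possible source of the number. Neither point rescues the sentence. Four interims are planned, and the two-sided reading spends only 0.108 at the 6-point hypothesis, against the one-sided 0.20 in both documents and the cumulative 0.200 in Table 3.

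A second argument is that crossing is not stopping. SAP 3.8 has the committee weigh the totality of the data, and about 1.7 of the 4.8 points arise at the 600-subject look. This stands as a condition on the figure, but the SAP's 0.6% makes no stated allowance for discretion, and the three earlier looks alone give about 3%.

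Third, the planned statistic is a Mantel-Haenszel difference stratified by pooled site, and the calculation here is unstratified. That is an untested assumption, but stratification would have to cut the crossing probability about eightfold to matter.

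Finally, the sentence is descriptive, and no boundary, look or test depends on it. That is correct and limits the weight of the point.

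**Conclusion.** The sentence is wrong as written. At 16% vs 24%, the chance of crossing the futility boundary at one of the four planned interims is about 4.8%. The loss of power is about 0.6 percentage points. That the second number was reported under the first one's name is a likely explanation, not an established one.

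The result assumes equal arms at each look, interims exactly as planned, no strata, no missing day 28 status, the rule followed whenever crossed, and no efficacy stop. The error is in a stated operating characteristic, not in the design: the boundary, the sample size, the design power and the description of the power effect as small all hold. It should be corrected, because it understates how often the rule would end the trial under the assumed benefit.

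**What to change.** Replace the 0.6% sentence in SAP Section 5 with wording such as:

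> *If the true difference is 8% (16% vs 24%), the looks occur as planned and the rule is followed, the chance of crossing the futility boundary at an interim is about 4.8%, and overall power falls by about 0.6 percentage points.*

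The sponsor may prefer to recompute both figures with the stratified statistic before printing them; about 5% is the size to expect for the crossing probability.

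An optional clarification is to label the interval column of Table 3 as one-sided lower confidence bounds. The two-sided equivalents, 1 minus twice the printed nominal alpha, are 99.4%, 93.0%, 84.6%, 77.6% and 69.0%.

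The cost is one sentence and, if wanted, one column header. The looks, the alpha, the -0.06 criterion and the boundary do not change.

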## 7 APPENDIX

### 7.1 Appendix A

#### Adverse Events

If onset date is completely missing, onset date is set to date of first dose.

If (year is present and month and day are missing) or (year and day are present and month is missing):

    If year = year of first dose, then set month and data to month and day of first dose

    If year < year of first dose, then set month and day to December 31.

    If year > year of first dose, then set month and day to January 1.

If month and year are present and day is missing:

    If year = year of first dose and

        If month = month of first dose then set day to day of first dose

        If month < month of first dose then set day to last day of month

        If month > month of first dose then set day to first day of month

    If year < year of first dose then set day to last day of month

    If year > year of first dose then set day to first day of month

For all other cases, set onset date to date of first dose.

#### Prior and Concomitant Medications

Impute partial/missing start date with earliest possible date, and end date with latest possible date.

If start date of medication is completely missing in which the day, month, and year are all unknown or only the day is known, then the start date will not be imputed.

For the partial start date of medication,

- If the year is present and the month and day are missing or the year and day are missing, set month and day to January 1
- If the year and month are present and the day is missing, set day to 1st day of month.
- If the imputed start date of medication is after the non-imputed end date of medication, then the start date will be set to the end date of medication.
- 

If the end date of medication is completely missing, in which the day, month, and year are all unknown or only the day is known, then the end date will not be imputed.

For the partial end date of medication,

- If the year is present and the month and day are missing or the year and day are present and the month is missing, set month and day to December 31.
- If the year and month are present and the day is missing, set day to last day of the month.

Medications with both missing start and end date after imputation will be considered as both prior and concomitant medications.

## 7.2 Appendix B

**Table 4 Extreme Low and High Values for clinical labs**

Ranges	Unit	Values outside this range are considered extreme
Blood count		
Hemoglobin	g/dl	6 – 18.3
Hematocrit	%	18 – 55
White blood cells	10  /μL	3 - 30
Neutrophils	%	40 – 97
Eosinophils	%	none – 5
Basophils	%	none – 3
Lymphocytes	%	3 – 40
Monocytes	%	none – 9
Bands	%	none – 25
Blasts	%	none – 3
Atypical Lymphocytes	%	none – 10
Platelets	10  /μL	30 – 800
Blood Chemistry		
Sodium	meq/L	120 -155
Potassium	meq/L	2.2 – 6.5
Chloride	meq/L	85 - 120
Bicarbonate	meq/L	10 – 45
Glucose	mg/dL	40 - 400
Calcium	mg/dL	6 – 13
Urea/Bun	mg/dL	2 – 100
Creatinine	mg/dL	0.2 – 10
ALT	U / L	1-800
AST	U / L	1-800
Alkaline Phosphatase	U / L	10-800
Lactate Dehydrogenase	U / L	5 – 1500
Total bilirubin	mg/dL	0.1 - 5.0
INR	ng / ml	0.5 – 4
D-Dimer		500 – 10,000
Fibrinogen	mg / dl	100 - 800
